9.6 Heterogeneity of treatment effect (HTE)

HTE analyses will be hypothesis-generating, with the goal of identifying populations of patients for whom a recommendation for PRN follow-up is particularly effective. HTE analyses will evaluate the consistency of treatment effects on the primary outcome across the four types of infection, as well as patient race, ethnicity, finacial and social hardship, and use of telehealth for follow-up. The log-binomial generalized linear model for the primary outcome will be repeated for each subgroup. In addition, for each subgroup factor the log-binomial model for the full cohort will be extended by including interaction terms between the randomized treatment and the subgroup factor. The results of these subgroup analyses will be displayed by a forest plot containing risk ratios with 95% confidence intervals for each subgroup, with interaction p-values displayed on the plot.

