BeneFIT RCT demonstrates promise of PRN follow-up for one common pediatric infection. Our team completed an RCT comparing PRN vs. automatic follow-up, called the Bronchiolitis Follow-up Intervention Trial (BeneFIT).²³ BeneFIT was a multicenter trial conducted across 4 hospitals. Bene-FIT participants were 304 children hospitalized for a common infection called bronchiolitis. Results from BeneFIT are presented in Table 2. Four-fold fewer families attended post-hospitalization follow-up visits in the PRN group (19%) compared to the automatic group (81%). Both groups otherwise had similar outcomes, including no significant differences in parent anxiety, symptom duration, or readmission.

Outcome	PRN N = 138	Automatic N = 131	Absolute Difference (95% CI)
Attendance of a follow-up visit, n (%)	26 (19)	106 (81)	-63 (-53 to -72)
Parent anxiety score, a mean	3.9	4.2	-0.3 (-1.0 to 0.7)
Days to symptom resolution, mean	10	11	-1 (-3 to 1)
Readmission, n (%)	3 (2)	5 (4)	-2 (-6 to 2)

Table 2: Results of the BeneFIT RCT

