3.3 Study Process Measure

The proportion of participants who attend a follow-up visit (in-person or via telehealth) within 7 days of hospital discharge will be reported but will not be categorized as a formal outcome. Rather, the proportion of participants who attend a post-hospitalization follow-up visit will be a study process measure. A prior trial demonstrated that randomization to a recommendation of PRN vs automatic follow-up does result in a large difference in follow-up visit attendance.²³ We hypothesize that recommendations for PRN vs automatic follow-up in FAAN-C will similarly result in large differences in follow-up visit attendance.

4 Study Outcomes

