6.1 Treatment of Subjects

At the time of hospital discharge, families will be randomly assigned to either PRN or automatic follow-up recommendations as described below:

PRN follow-up: "You do not need to schedule a follow-up visit with your child's regular doctor today. If your child's illness continues to improve, you do not need to have a visit with your child's regular doctor within the next 7 days. If your child's illness does not seem to be getting better or you develop any new concerns, we recommend that you contact your child's regular doctor to discuss whether a follow-up visit might be necessary."

Automatic follow-up: "Please schedule a follow-up visit with your child's regular doctor before leaving the hospital. Please schedule the visit to occur within the next 7 days and plan to attend the visit even if your child's illness is getting better."

The automatic follow-up instructions are aligned with proposed quality metrics⁴⁰ and previous studies of automatic follow-up.^{25, 26, 28, 32, 34} Both the PRN and automatic follow-up instructions were utilized successfully for our prior trial, BeneFIT.²³

Pragmatic features of comparators. Pragmatic features that will make findings from FAAN-C more generalizable and quickly scalable include the following: 1) Follow-up visits, whether automatic or deemed necessary in the PRN group, can be conducted either in-person or via telehealth. The decision about whether a visit should occur in person or via telehealth will be at the discretion of families and their medical providers. 2) Beyond randomization to either PRN or automatic post-hospitalization follow-up recommendations, FAAN-C is not otherwise prescriptive for a participant's medical care. Hospitalists have complete autonomy about the patient's care while hospitalized, and PCPs have complete autonomy for the patient's care after hospitalization. 3) Beyond embedding follow-up instructions in the electronic health record, the discharge process is otherwise preserved according to each hospital's usual procedures.

7 Treatment Assignment Procedures

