8.4 Randomization Process

Randomization will occur when study staff learn that hospital discharge for the study participant is likely to be that day and/or discharge orders have been placed. Prior to randomization, study staff will complete an enrollment checklist in REDCap. The enrollment checklist will verify that all necessary pre-randomization items have been completed. When the enrollment checklist is complete, REDCap will supply the study staff with the patient's randomization assignment. Study staff will notify the patient and their parents of their randomization assignment and their recommended follow-up strategy (PRN or automatic follow-up). Study staff will also communicate the participant's randomization assignment to the participant's inpatient medical team and PCP.

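### Section 9.6 uses telehealth use, which is settled after randomisation and depends on attendance, as a subgroup factor, so the arm comparison within it is not randomised

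*Protocol*

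**What the plan says.** Section 9.6 of the protocol studies consistency of the effect on 14-day readmission across the four infection types "as well as patient race, ethnicity, finacial and social hardship, and use of telehealth for follow-up". For each factor the primary log-binomial model is refitted within every subgroup and a treatment-by-factor interaction is added to the full-cohort model. Risk ratios and interaction p-values go on one forest plot. The stated status and aim are: "HTE analyses will be hypothesis-generating, with the goal of identifying populations of patients for whom a recommendation for PRN follow-up is particularly effective".

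Four other places bear on the telehealth factor:

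- **Timing of assignment (8.4):** "Randomization will occur when study staff learn that hospital discharge for the study participant is likely to be that day", or once discharge orders are placed.
- **Choice of visit mode (6.1):** "The decision about whether a visit should occur in person or via telehealth will be at the discretion of families and their medical providers".
- **Reason for a visit (6.1):** the PRN script prompts contact with the regular doctor conditionally: "If your child's illness does not seem to be getting better or you develop any new concerns". The automatic script tells families to "plan to attend the visit even if your child's illness is getting better".
- **Effect of assignment on visits (3.3):** "We hypothesize that recommendations for PRN vs automatic follow-up in FAAN-C will similarly result in large differences in follow-up visit attendance". Section 2.1 gives 19% (PRN) and 81% (automatic) from the earlier trial.

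Section 9.6 does not define telehealth use as a baseline characteristic.

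**The concern.** A subgroup comparison keeps the protection of randomisation only if subgroup membership cannot be altered by assignment. Infection type, race, ethnicity and hardship meet that condition. Telehealth use does not, because it follows assignment and requires a visit that assignment is meant to make more or less likely.

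The two scripts also tie attendance to clinical course differently. PRN attenders are likely to include a high proportion of children who are not recovering well; automatic attenders should be closer to a cross-section. In addition, a child readmitted before any visit may never have the chance to use telehealth, so membership can depend on the outcome itself.

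At stake is one part of the forest plot and one interaction p-value. A reader could take them as a lead on whether telehealth changes the effect of PRN follow-up, when selection alone could have produced them.

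**Working it through.** **1. The plan's own figure, used for the denominators.** Section 9.9 assumes 3.5% readmission in both arms, a margin of 2.5 points, one-sided alpha 0.025, 90% power and 15% attrition.

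n per arm = (1.960 + 1.282)² × 2 × 0.035 × 0.965 / 0.025² ≈ 1,136 with outcome. Then 1,136 / 0.85 ≈ 1,337 randomised per arm, or 2,674 in total. This matches the protocol.

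**2. Order of events.** Randomisation around discharge (8.4) → PRN or automatic script (6.1) → visit or no visit, which differs by arm (3.3) → choice of mode (6.1). The subgroup factor is the last step in this chain.

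**3. Illustration with no true effect.** From the protocol: 3.5% readmission in both arms; attendance 19% and 81%. Assumed, because the protocol gives no values:

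- 20% of children are not improving, with readmission risk r1 between 6% and 12%;
- these children make up a share s of PRN attenders, between 30% and 80%;
- automatic attenders are a cross-section, with risk 3.5%;
- visit mode is unrelated to clinical course;
- a share t of visits is by telehealth: 10%, 20% or 40%.

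Risk in improving children: r0 = (0.035 − 0.2 × r1) / 0.8. 
Risk in PRN telehealth users: u = s × r1 + (1 − s) × r0. 
Risk ratio among users: u / 0.035.

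| r1 | s | r0 | u | Risk ratio among users |
|---|---|---|---|---|
| 6% | 30% | 2.875% | 3.81% | 1.09 |
| 8% | 50% | 2.375% | 5.19% | 1.48 |
| 12% | 80% | 1.375% | 9.88% | 2.82 |

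**4. The comparison row.** If the reference is all non-users, including in-person attenders, PRN non-user risk = (0.035 − 0.19 × t × u) / (1 − 0.19 × t) and automatic non-user risk is 3.5%. Over the same ranges:

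| t | PRN/automatic risk ratio among non-users |
|---|---|
| 10% | 0.96 to 1.00 |
| 20% | 0.93 to 1.00 |
| 40% | 0.85 to 0.99 |

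If the reference is in-person attenders only, the same selection acts in both rows. In the middle case both risk ratios are 1.48, and the interaction is biased only if choice of mode also differs by arm and clinical course.

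**5. A second parameterisation.** Keep 20% not improving, let 60% of them attend in the PRN arm, and set attendance among the others to (0.19 − 0.2 × 0.6) / 0.8 = 8.75%. If non-improving children have 2, 3 or 5 times the risk of the others, the ratio among telehealth users is 1.36, 1.62 or 1.96. At a risk multiple of 1 it is 1.00, as it should be.

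**6. Precision at t = 20%.** Users: 1,136 × 0.19 × 0.2 ≈ 43 PRN and 1,136 × 0.81 × 0.2 ≈ 184 automatic, so the 1:1 balance is lost. In the middle case the expected readmissions are 2.24 and 6.44. SE of the log risk ratio = √(1/2.24 − 1/43 + 1/6.44 − 1/184) ≈ 0.76, giving an approximate 95% interval of 0.34 to 6.5 around 1.48.

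**The case against.** - **It is only exploratory.** Section 9.6 says so, and no confirmatory claim rests on this row. This stands and limits the weight of the point. The label warns about multiplicity and strength of evidence; it does not make non-comparable groups comparable.
- **The bias would be lost in the noise.** With about 2 and 6 expected events, a shift to 1.48 is far inside the interval, and a model adjusted for site and infection type may not be estimable. This also stands: a firm misreading is unlikely. It is equally a reason not to plan the row.
- **The interaction need not be biased.** Correct where in-person attenders are the reference and mode is chosen alike in both arms. Section 9.6 does not name the reference. The comparison within telehealth users is compromised either way.
- **The numbers rest on assumptions.** They do. The upper figure of 2.82 implies that 0.8 × 0.19 / 0.20 = 76% of non-improving PRN children attend, at 12 / 1.375 = 8.7 times the risk of the others. If sicker children are steered to in-person visits, the distortion could shrink, or reverse if steering differs by arm. The figures show that bias can arise, not its likely size.
- **A statistical analysis plan could define the factor.** Possible, but use of telehealth for follow-up does not naturally read as a baseline measure of access, and nothing else in the protocol cures it. The instrumental variable analysis in 9.7 concerns attendance, not visit mode.

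**Conclusion.** The concern holds. As written, section 9.6 plans an arm comparison within a group formed after randomisation, by a process that assignment is expected to change and that the two scripts tie differently to clinical course. That conclusion rests on the protocol's text alone.

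The size is illustrative: a spurious risk ratio among telehealth users of about 1.5, anywhere from 1.09 to 2.82 under the stated assumptions, with the non-user row close to 1 at modest telehealth shares. The upward direction requires that non-improving children carry a higher readmission risk, are over-represented among PRN attenders, and are not kept out of telehealth by steering that differs by arm. Bias in the interaction depends on the reference group.

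The consequence is confined to one factor in a hypothesis-generating analysis. It should be corrected, but it does not threaten the trial's main conclusions.

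**What to change.** Delete telehealth use from the factors in section 9.6. If the question matters, replace it with something fixed before randomisation, such as whether the clinic the family names offers telehealth, or the family's prior telehealth use. Either can be asked in the parent interview, which section 8.3 already places before randomisation. Such a factor answers a different question, about access or habit rather than use, but it can be known when the recommendation is given.

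Report actual telehealth use by arm descriptively, with the attendance process measure in section 3.3, which already counts telehealth visits. Keeping the row with a non-randomised label would be weaker, since the same ratio and p-value would still sit beside those for true baseline factors.

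The cost is one deleted phrase and, optionally, one interview item. That item would be missing for any child enrolled before it is added. No endpoint, sample size or clinical procedure changes.

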9.7 Instrumental variable analysis

We will supplement the ITT analysis with an instrumental variable analysis, which is a type of per-protocol analysis and is a recommended component of non-inferiority trials.^{67, 68} We will use randomization as the instrument to approximate the average causal effect on patient outcomes of actually attending a post-hospitalization follow-up visit. While the ITT analysis evaluates the average effect of assigning subjects to a recommendation for PRN vs automatic follow-up in the full cohort, an instrumental variable analysis estimates the average effect of actually receiving a follow-up visit among patients who would attend the visit if assigned to an automatic follow-up recommendation, but not if assigned to a PRN follow-up recommendation. The instrumental variable analysis depends on two key assumptions: 1) the randomized treatment influences outcomes only through the effect of treatment assignment on the occurrence or nonoccurrence of a follow-up visit, and 2) randomization to a PRN follow-up recommendation does not cause any subjects to attend a follow-up visit when they would not have done so if randomized to an automatic follow-up recommendation.⁶⁹

9.8 Missing Data

We will use multiple imputation based on fully sequential imputation with predictive mean matching to impute missing data. Multiple imputation will be particularly useful because we expect to have strong auxiliary variables—that is, variables that are highly correlated with study outcomes and risk of missingness. Auxiliary variables we will utilize include patient demographic factors (e.g., race, ethnicity) measures of illness severity (e.g., length of stay, disease-specific characteristics), and hospital readmission documented in the electronic medical record.

9.9 Sample Size and Power

The RCT will be powered for non-inferiority of a recommendation for PRN follow-up compared to automatic follow-up for the primary outcome, 14-day all-cause hospital readmission. In 2019, the mean 14-day all-cause readmission rate across FAAN-C sites among patients who would meet inclusion criteria for FAAN-C was 3.5% (extracted from the Pediatric Health Information Systems database on April 29, 2020). Given that automatic post-hospitalization follow-up is recommended to the majority of hospitalized children, we used 3.5% as the estimated readmission rate for the automatic post-hospitalization follow-up group. We set the non-inferiority margin at 2.5% because hospitalists and PCPs reported in focus groups that they would consider a recommendation for PRN follow-up to be inferior to a recommendation for automatic follow-up if the PRN follow-up recommendation resulted in a more than 2–3% absolute increase in hospital readmissions. At a margin of 2.5%, the parents of 40 children would need to be instructed to have automatic follow-up visits before 1 hospital readmission would be prevented (that is, the number needed to treat⁷¹ =40). If \geq 40 parents would need to be instructed to have automatic follow-up to prevent a hospital readmission, we will conclude that a recommendation for PRN follow-up is non-inferior to a recommendation for automatic follow-up. We assume that the primary outcome will be available

for at least 85% of subjects (15% attrition). Under these assumptions, a total sample size of 2,674 patients (1,337 patients in each group) will provide 90% power with 1-sided α =0.025 to demonstrate non-inferiority of a recommendation for PRN follow-up. We defined the non-inferiority margin without adjusting for non-compliance for two main reasons. First, patients randomized to a recommendation for PRN follow-up are compliant whether or not they choose to attend a follow-up visit. Secondly, the assumed readmission rate for the automatic follow-up group (3.5%) is derived from a sample from which non-compliance occurred. Non-compliance is expected to be greater outside of a trial setting, which preserves our conservative power estimate.

10 Data Management

10.1 Study Monitoring

The investigators recognize the importance of ensuring data of excellent quality. Study monitoring is critical to this process. Monitoring has been a very effective tool for maintaining data quality in previous studies, and we will utilize this process to ensure excellent quality data in the proposed study. The Data Coordinating Center utilizes risk-based methodology to identify and correct problems that may arise at sites. The risk-based approach to monitoring focuses on oversight activities and preventing or mitigating key risks to data quality, as well as to processes critical to human subject protection and integrity of the trial or study.

Study monitors must be provided with appropriate access to study materials and the medical records for study subjects. If the medical records are in electronic form, the clinical investigator or an authorized individual must provide any assistance necessary to facilitate the study monitor's review of data in the electronic medical record.

10.1.1 Site Monitoring Plan

A supplemental study-specific risk-based monitoring plan, separate from the protocol will be completed which outlines specific criteria for monitoring. This plan may include the number of planned site visits, criteria for focused visits, additional visits or remote monitoring, a plan for chart review and a follow-up plan for non-compliant sites. The monitoring plan also describes the type of monitoring that will take place (e.g., sample of all subjects within a site; key data or all data), the schedule of visits, how they are reported and a time frame to resolve any issues found.

10.1.2 Clinical Site Monitoring

Site monitoring visits may be performed during the study period to ensure regulatory compliance, patient safety, and to monitor the quality of data collected. Essential document binders, regulatory documents and data collection forms may be reviewed. The site monitor will provide each site with

a written report, and sites will be required to follow-up on any deficiencies. The site initiation may take place as group training made up of site investigators and research assistants.

10.1.3 Remote Monitoring

The Data Coordinating Center may supplement on-site monitoring with remote monitoring activities. Remote monitoring involves detailed review of the data entered by each site and consultations with each site investigator and/or research coordinator to review safety and data quality. This may require uploading copies of medical records, patient study files, regulatory documentation, or other source documents for the monitor to review. Alternatively, other methods, such as remotely viewing source documentation, may be utilized. This helps assure protocol compliance and accurate data collection. The Data Coordinating Center may conduct more remote monitoring activities early in the trial to assure protocol compliance and identify any training issues that may exist. Remote monitoring documents will be retained in accordance with federal requirements. Safety of subjects will be monitored and ensured in accordance with the Data and Safety Monitoring Board (DSMB) plan.

10.2 Record Access

The medical record and study files (including informed consent, permission, and assent documents) must be made available to authorized representatives of the Data Coordinating Center, upon request, for source verification of study documentation. In addition, medical information and data generated by this study must be available for inspection upon request by representatives (when applicable) of the, NIH, other Federal funders or study sponsors, and the Institutional Review Board (IRB) for each study site.

11 Protection of Human Subjects

11.1 Institutional Review Board (IRB) Approval

The Institutional Review Board (IRB) at the University of Utah will serve as the single IRB. The Utah IRB has extensive experience with single IRB implementation due to our participation in the NCATS funded Trial Innovation Center, which has implemented over 35 SIRB studies, several with EFIC.

In addition to SIRB activities, each institution has Human Research Protection activities that will be completed prior to site activation. These include conflict of interest, assuring competence of investigators, impact on hospital services, etc., and are individualized to each site.

The Data Coordinating Center will track IRB approval status at all participating centers and will not permit subject enrollment without documentation of initial IRB approval and local review

sign-off. The Data Coordinating Center will also track the maintenance of that approval throughout subsequent years of the project.

11.2 Informed Consent Process

SIRB procedures should be well understood by all research staff and clearly documented in the Essential Documents Binder or eBinder.

GCP Reminder (Informed consent advice from OHRP): Informed Consent is a process, not a form. Information must be presented to enable the person to voluntarily decide whether or not to participate as a research subject. It is a fundamental mechanism that ensures respect for persons through provision of thoughtful consent for a voluntary act. The procedures used in obtaining informed consent should be designed to educate the subject population in terms that they can understand. Think of the document primarily as a teaching tool not as a legal instrument. http://www.hhs.gov/ohrp/regulations-and-policy/guidance/informed-consent/index.html

The informed consent process can be a collaborative effort between research staff, the site PI and Co-PIs, and clinicians. However, if the site PI/Co-PI are unavailable research staff may introduce the study and proceed through the informed consent process. A PI or CO-PI should always be available by phone to the research staff to answer any additional questions the family may have as needed in the rare case that the research staff is unable to answer specific questions.

